9.8.1 Independent Safety Monitor (ISM)

The ISM is a physician located near each respective investigator site with relevant expertise whose primary responsibility is to provide independent safety monitoring in a timely fashion. This ISM is identified by the investigator site and approved by DMID. The ISM will review all SAEs as submitted by the clinical site and other AEs as needed and provide an independent written assessment to DMID for each SAE. The study site will have an ISM with experience in infectious diseases or internal medicine.

9.8.2 Safety Monitoring Committee (SMC)

This clinical trial will utilize an SMC, which is an independent group of experts that advises DMID. The primary responsibility of the SMC is to monitor subject safety. The SMC is external to DMID and composed of at least three voting members. The SMC will consist of members with appropriate expertise to contribute to the interpretation of the data from this trial. Its activities will be delineated in a SMC charter that will describe membership, responsibilities, and the scope and frequency of data reviews. The SMC will operate on a conflict-free basis independently of the study team. DMID or the SMC may convene ad hoc meetings of the SMC according to protocol criteria or if there are concerns that arise during the study. All reviews by the SMC will be performed with blinded data, unless otherwise requested by the SMC chair. If unblinded data are requested, the SMC will review the unblinded data in a closed session.

The SMC review of all safety and PK data after completion of each cohort. The SMC will also be consulted on an *ad hoc* basis if halting criteria are met, when recommendations are sought for clinical findings, and to recommend dose escalation.

10 CLINICAL MONITORING

All clinical monitoring activities will be conducted in accordance with ICH/GCP, applicable Parts in Title 21/45 of the CFR, and DMID requirements for the clinical monitoring of the study conducted under Contract No. Phase 1 DMID HHSN272201100030C.

10.1 Site Monitoring Plan

A Clinical Research Associate (CRA) will be responsible for the clinical monitoring of the study. This CRA will remain blinded throughout the study and will perform scheduled visits to verify that the clinical trial is being conducted and data are generated, documented (recorded), and reported in compliance with the protocol, GCP, and the applicable regulatory requirements. A monitoring plan will be developed commensurate with the degree of potential risk to study subjects and the complexity of the study. Reports will be submitted to Emergent on monitoring activities. The site will provide direct access to all trial-related source data/documents, and reports for the purpose of monitoring and auditing by the Sponsor and their designees, and inspection by local and regulatory authorities and their designees. The [REDACTED] Phase 1 Unit Clinical Research Coordinator will work closely with the CRA and will attempt to address the issues that are raised. The site PI is ultimately responsible for ensuring that the monitor's findings are addressed. The review of study records will be performed in a manner to ensure that subject confidentiality is maintained. There will also be an unblinded CRA responsible for product reconciliation as required throughout the study.

Monitoring procedures outlined in the Emergent -approved site monitoring plan will be followed in order to comply with [Section 10](#).

11 STATISTICAL CONSIDERATIONS

11.1 Study Hypotheses

Not applicable.

11.2 Sample Size Considerations

The study will enroll 8 subjects in each cohort for up to 5 cohorts. In each cohort, 6 subjects will be randomized to receive UV-4B and 2 will receive placebo. The number of subjects within each dose group was chosen based on historical experience with safety trials.

11.3 Planned Interim Data Review

After completion of the third cohort, a summary report will be provided to the SMC, including tables and listings of all data for each cohort. Recommendations from the SMC along with safety and PK data will be provided to the FDA after the completion of each cohort. All data will remain blinded. Initiation of dosing in subsequent cohorts will occur only after assessment of safety and plasma PK parameters from the previous cohort have been completed.

11.3.1 Safety Review

A blinded report with tables and listings including AEs will be provided to the SMC after each cohort.

11.3.2 Efficacy Review

Not applicable.

11.3.3 Pharmacokinetic Review

Pharmacokinetic parameters will be analyzed as described in [Section 11.4.6](#). The PK data will be reviewed after each cohort.

11.4 Final Analysis Plan

11.4.1 Populations for Analysis

The safety population will be defined as all subjects who receive study product or placebo.

The PK population will consist of all subjects who receive study product, and have measurable values, and complete scheduled post-dose PK measurements without protocol

deviations, violations, or events thought to significantly affect the PK of the drug. In the case of a significant protocol deviation, PK data collected during the affected treatment period will be excluded from the analysis. Examples of significant protocol deviations or events include, but are not be limited to: vomiting following oral dosing occurring within 30 minutes, sample processing errors that lead to inaccurate bioanalytical results, and/or inaccurate dosing on the day of PK sampling.

11.4.2 Randomization and Stratification

Subject data will be analyzed according to treatment administered, as is standard for early clinical studies, due to the focus on safety and PK data. No stratification is planned for this study.

11.4.3 Procedures for Handling Missing, Unused, and Spurious Data

All available scheduled visit data will be included in data listings and tabulations. In addition, unscheduled visit data will be included in data listings. No imputation of missing values will be performed. Percentages of subjects with AEs or laboratory toxicities will be based on non-missing values. Data that are potentially spurious or erroneous will be examined under the auspices of standard data management operating procedures.

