7.6 Unscheduled Visits

Data from unscheduled visits or procedures (if any) will be captured in the EDC system and presented in data listings. These data will be clearly identified as unscheduled observations. Safety assessments including updated history and the following onsite evaluations: AE, PE, and any other study procedures deemed necessary by the PI will be obtained.

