10.1.1 Unscheduled Readings

Unscheduled readings are defined as readings collected >15 minutes from the actual time of the original reading. Where results are taken in triplicate, the original reading is defined as the first reading of the triplicate. Unscheduled readings are labelled as 'Unscheduled' in the listings.

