10.7.4 Clinical Laboratory Parameters

Observed values and change from baseline data for clinical laboratory parameters (hematology, serum chemistry, coagulation, urinalysis) will be summarized by treatment. Baseline is considered as the last laboratory test result collected before the first dose.

Shift tables will be presented for serum chemistry, hematology, coagulation, and urinalysis parameters according to laboratory toxicity grading. The grading of laboratory findings was based on the *FDA Guidance for Industry: Toxicity Grading Scale for Healthy Adult and Adolescent Volunteers Enrolled in Preventive Vaccine Clinical Trials September 2007* and *Division of Microbiology and Infectious Diseases (DMID) Adult Toxicity Table November 2007* as modified for this study (found in Appendix II of the protocol). A summary of clinical laboratory values of toxicity Grade 1 or higher will also be provided by parameter and treatment.

Individual subject data listings (serum chemistry, hematology, coagulation, and urinalysis) will be provided to summarize all laboratory values including change from baseline, all laboratory values outside the clinical reference ranges, and all laboratory values of toxicity Grade 1 or higher.

Values for any serum chemistry, hematology, coagulation, and urinalysis values outside the clinical reference ranges and also meeting toxicity grading criteria will be flagged on the individual subject data listings.

Fecal and vomitus occult blood findings will be summarized and listed by treatment and study day.

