10.7.5 Vital Signs

Routine vital signs data (systolic and diastolic blood pressure, pulse rate, respiratory rate, and oral temperature) and orthostatic vital signs data (blood pressure and pulse rate) will be listed and summarized by treatment, along with changes from baseline, where baseline is defined as the last value prior to the first dose on Day 1, including unscheduled values. Orthostatic change is the standing value minus the supine value taken prior to the standing value.

A summary of vital signs values of toxicity Grade 1 or higher will also be provided by parameter and treatment. The grading of vital signs was based on the *FDA Guidance for Industry: Toxicity Grading Scale for Healthy Adult and Adolescent Volunteers Enrolled in Preventive Vaccine Clinical Trials September 2007* as modified for this study (found in Appendix II of the protocol).

For routine vital signs data, values outside the clinical reference ranges will be flagged on the individual subject data listing, as will the vital sign values meeting toxicity Grade 1 or higher.

The reference ranges for routine vital signs are: supine systolic blood pressure (90-140 mmHg), supine diastolic blood pressure (50-90 mmHg), supine pulse rate (40-100 bpm), respiratory rate (10-24 breaths/minute) and oral temperature (35.5°C -37.8°C).

Orthostatic decreases of ≥ 20 mmHg for systolic blood pressure or ≥ 10 mmHg for diastolic blood pressure or an increase in heart rate of > 30 bpm are considered to be of potential clinical concern and will also be highlighted on the individual data listings. Repeat and unscheduled readings will be handled as defined in Section 10.1.1.

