10.7.6 Electrocardiogram

Triplicate 12-lead ECGs will be collected at predose on Day 1 only, and a single ECG will be collected at all other scheduled times. The mean of these 3 values (including any unscheduled values) at Day 1 predose will be used in all subsequent calculations of changes from baseline.

The ECG data will be obtained directly from the 12-lead ECG traces. These data include the QTc interval calculated using the Fridericia correction (QTcF), the PR and QT intervals, QRS duration, and heart rate. ECG data will be reviewed by the PI or designee to determine abnormal results and their clinical significance.

The ECG data will be summarized by treatment, together with changes from baseline.

An outlier analysis will be performed of all individual postdose measurements, including all repeat and unscheduled readings. The frequency of subjects with a maximum increase from baseline in QTcF interval will be summarized for each treatment according to the following categories: > 450 ms (male) or > 470 ms (female); > 500 ms; change from baseline > 30 ms to ≤ 60 ms; and change from baseline > 60 ms. Additionally, PR duration > 220 ms and QRS duration > 120 ms will be summarized.

Individual subject ECG data will be listed. Values for ECG parameters outside the clinical reference ranges will be flagged on the individual subject data listing. The reference ranges are 50-100 bpm for heart rate, 120-210 ms for PR interval, ≤ 120 ms for QRS duration, 340-450 ms for QT interval, > 450 ms for QTcF interval. All incidences of QTcF > 450 , > 480 , and > 500 ms will be flagged on the individual subject listing. All incidences of QTcF change from baseline > 30 and > 60 ms will be flagged on the individual subject listing.

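### The laboratory toxicity-grade tables have no rule for unscheduled post-dose results, so they can understate a subject's worst grade

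*Protocol*

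**What the plan says.** Protocol 11.4.3 states the general rule: "All available scheduled visit data will be included in data listings and tabulations. In addition, unscheduled visit data will be included in data listings". Protocol 7.6 widens it from visits to procedures: "Data from unscheduled visits or procedures (if any) will be captured in the EDC system and presented in data listings".

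The SAP does not replace this rule for laboratory data. Section 10.1.1 defines the term ("Unscheduled readings are defined as readings collected >15 minutes from the actual time of the original reading") and gives one instruction: "Unscheduled readings are labelled as 'Unscheduled' in the listings". Section 10.7.4 plans shift tables by toxicity grade and adds: "A summary of clinical laboratory values of toxicity Grade 1 or higher will also be provided by parameter and treatment". It does not mention unscheduled values, and it does not say which post-baseline value a shift table uses. Section 12 declares no change from the protocol.

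Elsewhere the SAP is explicit when unscheduled values are to count. They count towards baseline (10.1) and towards the Day 1 pre-dose ECG mean. For ECG outliers, 10.7.6 says: "An outlier analysis will be performed of all individual postdose measurements, including all repeat and unscheduled readings".

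For vital signs, SAP 10.7.5 says: "Repeat and unscheduled readings will be handled as defined in Section 10.1.1". That section contains no rule for tables.

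**The concern.** Change in laboratory values is one of two primary outcome measures (Protocol 3.2.1), and the grade tables are where a reader will look for laboratory toxicity by dose. Unscheduled laboratory results are not a random subset. Protocol 9.2.3 provides for repeat tests to follow abnormal findings, so they arise mostly in subjects who have a problem. Leaving them out of a worst-grade display can lower a subject's grade or leave it unchanged. It can never raise it.

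The treatment is also uneven. An unscheduled pre-dose value can set the laboratory baseline, and an unscheduled post-dose ECG enters the outlier table although ECG is a secondary outcome. An unscheduled post-dose laboratory value has no stated route into a table.

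**Working it through.** The plan gives no figure to reproduce: the sample size has no statistical basis and no inferential safety analysis is planned. The check is therefore a trace of the rule, followed by its size.

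1. **Trace for laboratory values.** Protocol 11.4.3 and 7.6 name listings as the output for unscheduled data. SAP 10.1.1 labels such data in listings. SAP 10.7.4 is silent and SAP 12 declares no change. No step puts an unscheduled post-dose laboratory result into a table.

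2. **When it matters.** The tables are wrong for a subject only if the unscheduled grade exceeds every scheduled grade for that parameter. Full panels are scheduled daily on Days 2 to 8, then on Day 10 (±1) and Day 15 (±1) (Protocol 8.2.1). The nominal gap between the last two is 15 − 10 = 5 days. The windows allow 16 − 9 = 7 days at most and 14 − 11 = 3 days at least. A peak inside that gap can be seen only on an unscheduled draw.

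3. **Illustration (assumed values).** Take ALT at 4 × ULN on Day 10, 6 × ULN on an unscheduled Day 12 draw and 3 × ULN on Day 15. Appendix II sets Grade 2 at 2.6 to 5.0 × ULN and Grade 3 at 5.1 to 10 × ULN. The three values are Grades 2, 3 and 2. Tables built from scheduled draws show a maximum of Grade 2, although the Day 12 value is a Grade 3 finding under Protocol 9.6.

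4. **Size in a dose group.** There are 6 active subjects per cohort (Protocol 11.2). Suppose one subject's only Grade 3 value is unscheduled. Intervals are exact 95% (Clopper-Pearson).

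| Group | Counted | Omitted |
|---|---|---|
| One dose, n = 6 | 1/6 = 16.7% (0.4% to 64.1%) | 0/6 = 0% (0% to 45.9%) |
| Pooled placebo, 5 × 2 = 10 | 1/10 = 10.0% (0.3% to 44.5%) | 0/10 = 0% (0% to 30.8%) |

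For a zero count the upper limit is 1 − 0.025^(1/n); with n = 6 this is 45.9%. Protocol 11.4.3 bases toxicity percentages on non-missing values. If the subject also has no scheduled value for the parameter, the entry becomes 0/5 (upper limit 52.2%).

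5. **Do the AE tables fill the gap?** Protocol 9.2.3 requires any graded laboratory value after the first dose to be reported as an AE, and SAP 10.7.2 tabulates all treatment-emergent AEs. That tabulation is by maximum severity. Protocol 9.2.1 defines severity by interference with everyday activities and records toxicity grade separately. A Grade 3 ALT without symptoms could be classed as mild. No planned AE table uses grade.

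6. **Vital-sign timing.** Protocol 9.1.2 allows two repeats at intervals of 5 to 10 minutes. The second therefore falls 2 × 5 = 10 to 2 × 10 = 20 minutes after the original reading, on either side of the 15-minute limit in SAP 10.1.1. One protocol sequence can be split by timing alone.

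**The case against.** The best case against the point is that exclusion is inferred. Neither protocol section says that unscheduled data go to listings alone, and SAP 10.7.4 does not limit its summary to scheduled draws. SAP 10.7.6 tabulates unscheduled ECG readings while SAP 12 reports no change, which suggests the sponsor does not read 11.4.3 as a ban. The table shells, which might settle the matter, are a separate document not available here. This stands as a caution: the text is silent rather than prohibitive. But a programmer who follows the protocol's contrast between tabulations and listings would leave these values out, and the explicit ECG wording makes the laboratory silence more telling.

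It can also be said that no worst-grade table is planned, so nothing is biased. That is fair for the shift-to-worst table, which would be an addition. The Grade 1 or higher summary is planned, and the gap applies to it directly.

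Four stronger readings might be inferred, and the documents do not support them.

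- **That a value which halted the study disappears.** It is reported as an AE, which is itself a primary outcome. It appears in the listing of Grade 1 or higher laboratory values, and dose-limiting toxicities are listed (SAP 10.7.2). The SMC receives listings as well as tables (SAP 11), and halting acts on findings, not on final tables.
- **That the same defect affects vital signs as a primary outcome with shift tables.** Vital signs are secondary (Protocol 3.2.2), no vital-sign shift table is planned, and Protocol 11.4.5 says their abnormal values will be tabulated.
- **That a maximum over all vital-sign readings is the remedy.** Protocol 9.1.2 grades the AE on the least abnormal value when readings stay abnormal after two repeats. A maximum would give a table grade above the AE grade for the same sequence.
- **That the aPTT halting rule shows the loss.** The repeat there confirms a Grade 3 value usually already obtained at a scheduled draw, so omitting the confirmation would not ordinarily lower the worst grade.

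**Conclusion.** The concern holds for laboratory values. As written, the plan sends unscheduled post-dose laboratory results to listings and provides no rule that brings them into the grade shift tables or the Grade 1 or higher summary. A subject whose highest grade was unscheduled is understated there, and one such subject moves a dose-group entry by 16.7 percentage points. The AE tables do not correct this because they use another scale.

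The conclusion rests on the natural reading of Protocol 11.4.3 and 7.6 and on the absence of a contrary rule in the table shells. How often it would occur cannot be estimated from the documents; daily panels on Days 2 to 8 make it uncommon during dosing. It limits one set of displays and does not mean that safety data are missing. It should be settled before database lock.

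For vital signs, the only finding is that SAP 10.1.1 and 10.7.5 are not reconciled with Protocol 9.1.2 and 11.4.5.

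**What to change.** **Laboratory values.** In SAP 10.7.4, state that the Grade 1 or higher summary, and a shift table from baseline to worst post-baseline grade, use all post-dose results: scheduled, repeat and unscheduled. Keep by-visit means and changes to scheduled values. Footnote the number of unscheduled draws per treatment group, because subjects tested more often have more chances to show a high grade. Align Protocol 11.4.3 and 7.6 with this and record the change in SAP 12.

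**Vital signs.** Reconcile SAP 10.1.1 and 10.7.5 with the repeat sequence and grading rule in Protocol 9.1.2 and with the tabulation of abnormal values in Protocol 11.4.5. The readings of one repeat sequence should stay together whatever the elapsed minutes, and the grade in the table should agree with the grade of the AE.

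**Cost.** SAP wording, a short alignment of the protocol text, and modest table programming. No additional data are needed.

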11.4.4 Statistical Plan

A formal statistical analysis plan for the analysis and presentation of data from this study will be finalized before database lock.

11.4.5 Safety

Safety variables will be tabulated and presented for all subjects in the safety population, grouped by treatment. Placebo subjects will be pooled into a single treatment group for analysis. Exposure to study product and reasons for discontinuation of study treatment will be tabulated.

Safety evaluation of AEs will be based on the incidence, intensity, and types of AEs. Changes in the physical examination findings, vital signs, and clinical laboratory results will be documented on an AE form. AEs will be coded using the Medical Dictionary of Regulatory Activities (MedDRA®) AE coding system for purposes of summarization. All AEs occurring in the study will be listed in by-subject data listings. Treatment-emergent events will be tabulated, where treatment-emergent is defined as any AE that occurs after administration of the first dose of study product or that is already present prior to the first dose of study product and becomes more severe postdose. Treatment-emergent AEs will be tabulated by relatedness to study product and by maximum severity. Deaths, SAEs, and events resulting in study discontinuation will also be tabulated.

Observed values and change from baseline in clinical laboratory parameters will be summarized over the duration of the study. Shift tables will be produced for selected laboratory parameters. Observed values and changes in vital sign parameters and ECG intervals will be summarized over time in a similar fashion to laboratory parameters, and any abnormal values will be tabulated.

Summary statistics for continuous variables will include number of observations, mean, standard deviation (SD), median, minimum and maximum. Categorical variables will be summarized by the number and percent of subjects.

11.4.6 Pharmacokinetics

Pharmacokinetic parameters will be calculated by noncompartmental analysis using WinNonlin Professional® Version 5.2 or higher. All calculations for final plasma parameter analysis will be based on nominal sampling times. PK analysis will be performed at the completion of each cohort. The following PK parameters will be estimated:

- C_{\max}
- t_{\max}
- $AUC_{(0-\text{last})}$
- $AUC_{(0-8)}$
- $(AUC_{(0-24)})$
- $AUC_{(0-\infty)}$
- CL/F
- Vz/F
- $t_{1/2}$
- Accumulation ratio as defined by $AUC_{(0-8)}$ after the last dose divided by $AUC_{(0-8)}$ after the first dose

Plasma concentrations and plasma PK parameters will be summarized by cohort. PK parameters will also be presented in graphs as detailed in the SAP.

Dose proportionality of C_{\max} , $AUC_{(0-\text{last})}$, and $AUC_{(0-\infty)}$ will be assessed graphically and statistically using the power model approach with the logarithm of PK parameters $AUC_{(0-\infty)}$ and C_{\max} as the dependent variables and the logarithm of the dose as the independent variable: $([AUC_{(0-\infty)}, AUC_{(0-\text{last})}, \text{ or } C_{\max}] = \alpha * \text{dose}^{\beta})$.

